1. BACKGROUND AND INTRODUCTION

1.1. DISEASE/PROPOSED INTERVENTION BACKGROUND

The problem

People with severe mental illness (PWSMI) have a 13-30-year shorter life expectancy than the general population.¹⁻³ This is largely attributed to high rates of modifiable cardiometabolic risk factors such as smoking, hyperlipidaemia, hypertension, obesity, diet and sedentary lifestyle,^{4,5} which translates to high rates of chronic disease. As a result, PWSMI are six times more likely to die of cardiovascular disease and four times more likely to die of respiratory disease than the general public.⁶ The annual economic cost of premature comorbidity in this population necessitates better integrated care; primary care is considered ideal for managing multimorbidity.^{7,8} PWSMI have poor uptake of preventive care and proactive use of primary care due to a number of provider issues (e.g. stigma, poor communication) and consumer issues (e.g. cognitive difficulties, low health literacy).⁹ The higher mortality rate among PWSMI also requires urgent attention. The costs of treating PWSMI and premature death among people of PWSMI in Australia in 2016 was \$15 billion.¹⁰

The intervention

An online shared care plan will facilitate coordinated and planned care of consumers of mental health services “consumers” including management of risk factors and referral to allied health services and other relevant programs. It will be adapted from one used for consumers with long-term cancer patients in St George and the existing Mental Health Shared Care Checklist used in the SLHD Living Well Living Longer (LWLL program).¹¹ It will be based on the existing shared care plan used by SLHD, which is a paper form. The use of the existing shared care plan ensures the study is testing the difference between paper and online shared care plans rather than differences in the content of the plans. Functional specifications developed in consultation with mental health services (MHSs), general practitioners (GPs) and consumers in SLHD. The online shared care plan a) is interactive so the GP and MHS can review, edit and add to it (the consumer can view it); b) generates automated reminders for GPs, care coordinators and consumers; and c) enables MHSs to monitor completion and evaluate outcomes. The MHS care coordinators and peer support workers will assist the consumers and any nominated carers to access the INCA software and review their plans.

The RPA Virtual Hospital at SLHD will be available across all four teams. It will be used in the intervention for:

1. people who do not have a GP or not able to get to a GP - RPA VIRTUAL will fill the GP role
2. teleconsultations involving the GP, mental health care coordinator (MHC) and the consumer. This will save the MHC going with a patient to the GP.

The tasks for the consumer, the GP and the MHS in the intervention are presented in Figure 1.

[figure not shown]

Figure 1 Intervention flow chart

Context

SLHD has five Adult Community Mental Health 'Core' Teams. The four largest teams will be involved in the study: 2 in Western Sector, 2 in Eastern Sector.

Table 1 Mental health teams in the study

Western Sector Teams	Eastern Sector Teams
Canterbury	Camperdown
Croydon	Marrickville

The SLHD Living Well Living Longer shared care program used the ACI clinical redesign process in partnership with CESPHN to develop a collaborative model of shared care with GPs.¹² This has engaged over 330 GPs in providing shared care to over 1000 PWSMI, 736 of which remain active with the MHS at most recent count. Of those active shared care consumers, 512 have received a verified annual physical health check with their GP.

These innovations require change to existing routines in both MHSs and general practice, facilitated by quality improvement activities led by clinical champions.

Training and support will be provided on using the shared care software to the implementation teams, in collaboration with the existing GP shared care liaison clinicians within Sydney Local Health Service (SLHD)'s MHS, and CESPHN field support staff. Separately they will provide training and support to GP practices upon installing the

shared care software. This training will also address redesign of routine practices and be provided to medical staff, care coordinators and peer support workers. The training and redesign elements will be informed by our previous research providing both training and quality improvement in general practice in the prevention and management of long-term conditions and care of vulnerable populations.^{13,14} This includes the importance of interactive and peer learning. It is also consistent with the education and practice support program of partner CESPNN.

There are challenges in organising initial and review shared care consultations for PWSMI in general practice, with this requiring considerable time from the care coordinator and strong engagement from the consumer. Telehealth has been shown to enable better access to a range of health services.¹⁵ Telehealth consultations involving consumers, GPs and mental health providers have been increasingly used since the COVID pandemic and can be used in this trial to facilitate shared care.

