6.2. INVESTIGATION PLAN

The schedule of surveys and qualitative interviews with study participants is presented in Table 6.

Table 6 Schedule of participant surveys and interviews

		Baseline survey	3-month after usual shared care survey	3-month after usual shared care qualitative interview
Consumers	Intervention	✓	✓	✓
	Comparison	✓	✓	✓
Carers	Intervention			✓
	Comparison			✓
GPs	Intervention	✓	✓	✓
	Comparison	✓	✓	✓
MHS	Intervention			✓
	Comparison			✓

The schedule of visits and procedures is presented in Table 7.

Table 7 Study visits and procedures

Study procedures	Observation			Treatment					Follow up
	Enrolment via MHS	GP phone contact	Consumer survey interview	MHS creates online shared care plan before GP Visit 1	GP Visit 1 To create/review online shared care plan ideally with MHS	MHS reviews care plan initially and as needed	Other GP visits as required (optional telehealth with MHS)	Annual physical health check by GP	
Invitation to participate	X								
Participant Consent	X								
Telephone/face-face interview			X						X
GP Agrees		X							
Care plan developed				X	X	X			
Care plan implemented and reviewed					X		X	X	

If consumers consent, the research team will approach their GP to participate. If the GP agrees a summary of the consumer's previous care is sent and the GP is assisted to download and install the software for the e-care plan. The GP or the MHS staff create the standard care plan (depending on workload of the GP). If the GP creates the standard care plan, they invite the mental health team to edit or join the plan. If the MHS staff creates the shared care plan, they invite the GP to edit or join the plan. Then, the care coordinator reviews the care plan and makes adjustments to suit the consumer's individual care and include other providers involved in the care. Next, the consumer is invited and attends the GP. At each visit the tasks in the care plan are completed by the GP with or without involvement of the mental health team by telehealth. Results of tests are uploaded into the care plan. The consumer is able to view the care plan but not to edit it. The care coordinator is able to review the care plan and check if tasks have been performed and results of these. Consumer and provider are sent reminder for follow up visits.

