Recruitment	There could be a variety of reasons why a GP may choose not to participate, such as time commitment and variability of PC skills and having to learn to use a software programme.	The trial is based upon our experience of working with GPs to install the same software package (different shared care template) for working with cancer specialists and their cancer patients. This experience identified that the software was easy to use and worked seamlessly with existing clinical software. In fact, it saved time for the GPs as they no longer needed to send letters or faxes to specialist services. Even so, training was provided (and will be provided in this study) by the research team and the software company. In addition, a position has been funded to ensure GPs are adequately supported to use the new software.
Interviews	Consumer/carer research participant feels uncomfortable about engaging in the interview.	Consumer reminded that they can withdraw at any stage or take a break.

Interviews	Emotional responses activated during the interview	
If participants become distressed during the interview, researchers will provide basic support and inform the care coordinator that the consumer was feeling distressed and might need follow up. If this happens out of hours, the researcher will ask the consumer if there is somebody they should call who can provide support e.g., support worker, GP or carer. If the researcher is concerned about a participant's safety out of hours, they will contact the mental health line [name].
 
Support information is also provided on the PISCF.

Intervention	Consumer feels uncomfortable with information being shared between health care providers or participating in consultations via telehealth	Participants are reminded that participation in shared care and/or telehealth consultations is voluntary and they may withdraw at any time.
Intervention	Care plan does not meet all consumer's needs or their condition becomes more acute.	Consumers can access the care plan and ask their GP or the care coordinator to make changes to add additional roles or actions. GPs are informed how they can quickly escalate care if the consumer's condition becomes more acute or unstable.

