An economic evaluation of the online shared care intervention (SHAReD) compared to usual care will be undertaken using the healthcare viewpoint. All relevant healthcare resources and health effects/benefits for the intervention and usual care groups will be identified, accurately counted and valued.

The healthcare resources used for delivering the SHAReD intervention and usual care will be identified, collected/estimated by researchers or clinicians delivering care, and valued. For the SHAReD intervention group, these will consist of the time of clinicians to develop the SHAReD care training program for staff, consumers and GPs; the materials used during the training (e.g. printing, travel time); the time of the facilitators to provide the staff training; and estimates of the time involved in general practice from encounter data and tasks (setting up care plan, making changes to or updating the care plan, communication with Mental Health team); essential infrastructure used; new technology purchased and used; training and supervision time for SHAReD participants and GPs; key medical treatments as per the description of the SHAReD intervention (such as medical tests, pathology, and medications); and consumables. The eMR reports such as CMH011 Document Audit, AMH Current Clients and AMH Metabolic Monitoring may be accessed by AI [name] and AI [name] to identify any relevant healthcare items and costs. For both groups, the occurrence of hospital admissions, Emergency Department visits and other health service usage (such as ambulatory care) will be measured and valued. These data will be sought from the SLHD's

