patient data collection using medical record numbers (and eMR) and associated SLHD costings during the study. Costs attributable to the research will not be considered. Estimates of how the work of clinicians (and thus costs) has changed from the situation without the SHAReD intervention will also be explored during the focus groups. Variations in healthcare usage (such as hospitalisations and other medical treatment sought) and costs occurring later in the study (and up to 3 months post completion of the intervention) will be sought from SLHD eMR reports and the SLHD Performance Unit for cost of ED presentations and hospitalisations. The mean costs in the SHAReD intervention and usual care groups will be compared in addition to the mean health effects/benefits such as the care plan completion rate, quality of care received, clinical metrics, hospital admissions (and readmissions), hospital length of stay, and score on the utility-based and disease-generic quality of life measure (EQ5D-5L).^{30,31}

Having data on both the healthcare resource utilisation (costs) and health effects/benefits for the different groups will allow us to undertake a detailed cost-consequence analysis (CCA) – a first step for the economic assessment. CCA is a widely used form of economic assessment and recommended for reporting on health interventions with significant complexity and when there are multiple effectiveness measures such as programs/models of care seeking to address a range of clinical outcomes (Drummond et al 2005), and broad-reaching programs that have a range of health and non-health related effects needing to be quantified and assessed (NICE 2017). For this initial step of the economics work, the relevant costs and multiple outcomes will be calculated and presented in a disaggregated way which enables decision-makers to assess the relative importance of each component to the context they face. The comparator will consist of those consumers who did not receive the SHAReD intervention. Descriptive analysis will be used to estimate the total and mean costs (and standard deviations) associated with the intervention and usual care, as well as the effectiveness information (outcomes) and reported in a disaggregated manner.

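### The intervention cost list counts care-plan work only when general practice does it, although mental health service staff create, review, monitor and support the plan

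*Protocol*

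**What the plan says.** **Who does the work.** Section 1.1 states that "The MHS care coordinators and peer support workers will assist the consumers and any nominated carers to access the INCA software" and review their plans. Section 6.2 says "The GP or the MHS staff create the standard care plan (depending on workload of the GP"), and then that "the care coordinator reviews the care plan and makes adjustments to suit the consumer's individual care and include other providers involved in the care". Table 7 has separate columns for plan creation and plan review by the MHS. Table 8 in section 6.3 makes the care coordinator responsible for regular review of incomplete plan tasks.

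**What is costed.** Section 8.2 (costing component) takes a healthcare viewpoint and undertakes to count and value every relevant healthcare resource in both groups. It then sets out what the SHAReD delivery resources are made up of, worded as a full list and not as examples. Plan work enters as "estimates of the time involved in general practice from encounter data and tasks (setting up care plan", and the same parenthesis goes on to changing or updating the plan and communicating with the mental health team. MHS input is recognisable only in developing and giving the training.

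**Related statements.** Changes in clinicians' work, and the costs that follow, "will also be explored during the focus groups". Section 8.2 also says "Costs attributable to the research will not be considered", while Table 8 reports that "a position has been funded to ensure GPs are adequately supported to use the new software". On teleconsultation, section 1.1 expects that "This will save the MHC going with a patient to the GP".

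**The concern.** The list does not match the delivery model in the same protocol. Whether plan set-up is costed would depend on who happened to do it, and section 6.2 lets that vary with the GP's workload. Section 8.2 plans a cost per care plan completed, and hypothesis 4 claims cost-effectiveness and cost avoidance. A decision to extend the plan across the district, which section 1.2 foresees, needs the district's own staff time in the calculation. The amount may not be trivial: section 1.1 itself says that arranging shared-care consultations takes the care coordinator considerable time.

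**Working it through.** The protocol states no hours, wage or cost for this work, so there is no figure to reproduce. The check is a comparison of sections, followed by an illustration with assumed inputs.

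**1. Tasks against the section 8.2 list**

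- Creating the plan (GP or MHS, 6.2): listed as general practice time; not listed for the MHS.
- Reviewing and adjusting the plan (care coordinator, 6.2 and Table 7): changes and updates are listed for general practice only.
- Checking tasks (care coordinator, 6.2 and Table 8): not listed.
- Helping consumers and carers use INCA (coordinators and peer workers, 1.1): not named; an item for training and supervising participants might cover part of it.
- Communication between the services: listed from the general practice side only.
- Developing and giving training: listed.

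**2. Other places the time could be picked up**

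- Ambulatory care is valued in both groups, and sections 9.1 and 9.5 name the eMR reports and the STARS Community Ambulatory MH Report. These may hold contact time. No source is stated for non-contact work such as building, editing or checking a plan.
- Changes in clinicians' work are assigned to focus groups. Table 6 and section 9.4 schedule interviews only. Section 9.4 does ask about changes in work, but no step converts the answers into hours or dollars.

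**3. Effect on the gross cost**

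For a task of *t* hours at hourly cost *w*, the list records *t × w* if general practice does it and 0 if the MHS does it. The recorded cost per plan therefore falls as more plans are created by MHS staff, even when total effort is unchanged.

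**4. Effect on the incremental cost**

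Let *h₁* be MHS plan hours per intervention consumer and *h₀* the MHS hours in usual care that the online plan displaces (paper-plan work, accompanying visits). The uncounted increment is *w × (h₁ − h₀)*.

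Assumed, not from the protocol: *h₁* = 1 to 4 hours, *h₀* = 0 to 4 hours, *w* = AUD 50 to 100. The intervention arm is taken as half of the planned 500 consumers, 250.

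- Gross, lowest: 1 × 50 = AUD 50 per consumer; × 250 = AUD 12,500.
- Gross, highest: 4 × 100 = AUD 400 per consumer; × 250 = AUD 100,000.
- Net, highest: 100 × (4 − 0) = +AUD 400 per consumer; × 250 = +AUD 100,000.
- Net, lowest: 100 × (1 − 4) = −AUD 300 per consumer; × 250 = −AUD 75,000.
- Net when *h₁* = *h₀*: zero.

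The gross omission can only lower the recorded intervention cost. The net omission can have either sign.

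**The case against.** The strongest reply is that section 8.2 already covers this. It promises to count all relevant resources in both groups, and it lets clinicians delivering care supply the estimates, which would include MHS staff. It values ambulatory care from MHS records and separately plans a cost per person from the district and state health system viewpoint. The item for training and supervision could absorb some consumer help and some GP support. The mention of focus groups looks like a slip for the provider interviews. Detailed unit-time methods are often left to a later analysis plan.

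Much of this stands. The means to measure MHS time are largely in the plan, and it would be wrong to say that MHS staff time is ignored altogether. But the protocol itself fixes a list, and that list conflicts with both the general promise and section 6.2. Non-contact plan work still has no stated source or valuation. That is more than detail left for later.

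A reader might go further and infer that every incremental ratio and any cost avoided must look too favourable. The documents do not support that. The comparator is the same plan on paper (section 1.1), it also takes coordinator time, and that time is not itemised. Section 1.1 also expects a coordinator saving from teleconsultation, although this may differ little between arms because RPA Virtual is available to all four teams. Nor can a shift in cost per QALY be claimed: hours, wages and QALY gain are all absent, and the cost-effectiveness ratios are conditional on effectiveness being shown. That the funded GP-support position will be excluded as a research cost is likewise only a possibility; the text does not classify it.

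**Conclusion.** The point holds as an inconsistency in the costing plan. If the section 8.2 list is followed literally, the gross intervention cost, and a cost per completed plan built on it, risk understatement and depend on which service did the work. The incremental cost, the incremental ratios and the cost-avoidance result are unreliable, with the direction of bias open. The dollar range in the working shows only that the gross and net effects behave differently; it rests wholly on assumed hours and wages. The risk is smaller to the extent that ambulatory records capture MHS contact time. The matter affects a secondary, economic objective and not the primary endpoints, but the cost-consequence analysis is planned whether or not effectiveness is shown, so it should be settled before costs are assembled.

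**What to change.** In section 8.2:

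- Add MHS staff time to the costed resources: plan creation, review and adjustment, task checking, consumer and carer support, and GP liaison. Name care coordinators, shared care clinicians and peer workers.
- Measure and value the same tasks in the same way in both arms, using the paper-plan equivalents in the comparison arm.
- Take contact time from the STARS and eMR data already requested. Take non-contact work as counts of plans created and reviewed multiplied by staff-estimated unit times. State how double counting between the two will be avoided.
- State whether the funded GP-support position is an intervention cost or a research cost.
- Replace the reference to focus groups with the provider interviews scheduled in Table 6 and section 9.4, and say how hours will be obtained.

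The cost is revised wording and a short staff time estimate in both arms. The intervention cost may come out less favourable.

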1.2. RATIONALE FOR PERFORMING THE STUDY

Communication between GP and MHS presents an ongoing challenge, with no shared electronic records system. Phone calls are often impractical, and emails are rarely utilised due to privacy concerns, therefore services typically rely on fax or mail, with no verification that the person receiving the update either reviews it or uploads it to their own electronic record for further transparency.

Research with other long-term conditions suggests that effective sharing of care requires an interactive information system allowing team members to confirm acceptance of their roles, notify when tasks are due, track that tasks are completed and share information and results.^{16,17} Online shared-care systems can improve appropriate health-service use and reduce hospitalisations and have been demonstrated as feasible for conditions such as cancer and diabetes.¹⁸⁻²² Their adaptation to shared care of PWSMI has not yet been demonstrated.

The interactive online shared-care plan has been used for two years in cancer shared care in St George Hospital and evaluated for its feasibility and acceptability to providers and consumers in that context.^{23,24} A pilot study of its use with consumers on Clozapine is being developed in SE Sydney. Preliminary findings are that it is acceptable to consumers and providers and significantly enhances the consistency of care provided in general practice. However, it does require changes to work practices in both mental health services and general practice.

The innovation to be trialled solves key challenges in shared and integrated care of PWSMI. If successful, it will improve the quality of preventive care received by PWSMI through better communication and coordination between general practice and MHSs. If successful, the intervention will be rolled out across the SLHD and CESPNN.

